4.4. Plan for annual reporting of AEs

Based upon continuing review, all adverse events will be reported to the Clarian IRB annually in writing.

4.5 Study Withdrawal/Discontinuation

Participants may withdraw from the participation in the study at any time. This requires a written request to the principal investigator.

5 Statistical Considerations

Sample size calculation was performed assuming an estimated prevalence of 50% of MA ≥ 69 in the general patient population with ACS on clopidogrel referred for cardiac catheterization according to previous studies. It was assumed that switching to prasugrel would reduce the maximal clot strength in 60% of these patients with baseline MA ≥ 69 resulting in 20% prevalence of high tensile clot strength. Assuming a power of 0.8 and alpha 0.05 with a loss of 5% of follow-up, a sample size of 50 in each arm and a total sample size of n=100 was calculated accordingly.

6 Privacy/Confidentiality Issues

All information will be collected and kept on a customized database on computers of the investigators and on a secure network server at the Krannert Institute of Cardiology. Access to the database is password protected and computers will be kept in locked offices at the Krannert Institute and Wishard Hospital. Access to the offices housing the information is only available via keys possessed by the investigators. Only the listed investigators of the study will have access to review information and to analyze data. Data sent for analysis will be de-identified. The names of the patients will not be revealed if the results of this study lead to a publication.

The genetic information found through the course of the study will not be revealed to the study participants or their family members.

Blood samples are stored in a secured biospecimen storage facility that has secured access. Biospecimens are deidentified and do not allow identification of patients.

7 Follow-up and Record Retention

The study will last for at least 6 months after enrollment of the last study subject. Records and samples will be kept as required by the IRB and federal legislation and until completion of all study related analyses.

D. FACILITIES AVAILABLE

The cardiac catheterization laboratories at Wishard Hospital and Methodist Hospital will be used as study locations as required for the clinical care of the patients. Standard hospital care will be provided.

Laboratory analyses including platelet studies, thrombelastography, as well as DNA analysis will be performed in the laboratories of the Division of Clinical Pharmacology, Indiana University School of Medicine.

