Although increased P₂Y₁₂ receptor inhibition with prasugrel is more efficient in reducing ischemic events than clopidogrel, it also carries an increased risk for significant bleeding. Personalized treatment approaches should ideally be able to identify patients at need for higher or lower intensity of platelet P₂Y₁₂ inhibition in an attempt to optimize the risk/benefit ratio for each patient. However, currently only one study prospectively compared a personalized dosing approach of clopidogrel vs. standard dosing in 162 patients prior to coronary stenting [9].

In addition to the currently available antiplatelet drugs that inhibit ADP mediated platelet aggregation by inhibiting P₂Y₁₂, several oral thrombin receptor protease-activated receptor-1 (PAR-1) inhibitors (platelet thrombin receptor) have been developed. Two oral PAR-1 inhibitors have completed phase 2 clinical trials and the eventual addition of these drugs to standard dual antiplatelet therapy may in the future further increase bleeding risk for patients on several antiplatelet drugs. Theoretically, thrombelastography may provide an ideal methodology to identify patients at highest risk for thrombin mediated ischemic events or identify patients at risk of bleeding. In the surgical field, thrombelastography has been used successfully to predict postoperative bleeding risk and guide post surgical and trauma related transfusion requirements.

Currently controversy exists as to the optimal method to identify patients at risk for ischemic events after coronary interventions and several point of care assays measuring platelet inhibition are currently in use in large prospective clinical trials. These currently employed methods focus on the specific amount of ADP mediated platelet aggregation measured ex-vivo to guide risk prediction and intensity of P₂Y₁₂ inhibition by either dose adjustment of clopidogrel or switching therapy to prasugrel. Therefore, as a control group we will include a group of patients which will be assigned to prasugrel or clopidogrel therapy based on LTA measurements pre-cath using a cutoff that has been validated as a predictor of ischemic events in several other large studies [1].

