2.0 Enrollment/Randomization

The current study will be an open label study. Subjects will be enrolled among patients who are admitted with an acute coronary syndrome (unstable angina, non-STEMI) and who are being referred for coronary angiography and possible percutaneous coronary intervention. All study candidates must have received at least 300mg of clopidogrel loading dose since admission, or have been on clopidogrel 75mg daily for >5 days at time of enrollment.

Subjects will be enrolled before undergoing diagnostic angiography using written informed consent after screening for appropriate candidates. Patients will have the first study blood draw performed prior to coronary angiography. In case significant coronary disease is found and the patient proceeds with percutaneous coronary intervention, the patient will be randomized to either a TEG guided or LTA guided strategy. The subject will then be switched to prasugrel or continue on clopidogrel according to the results of the pre-cath TEG or LTA measurements. Patients in the TEG guided arm with high physical clot strength ($MA \geq 69$) will be assigned to prasugrel, whereas patients with lower clot strength ($MA < 69$) will continue on clopidogrel. This cutoff reflects the 50th percentile of clot strength based on data from a prior cohort of patients undergoing PCI and was determined as cutoff for ischemic risk in prior studies.

Patients in the LTA guided arm with high on treatment platelet reactivity to ADP ($PA > 42.9\%$) will be assigned to prasugrel, whereas patients with low on treatment platelet reactivity ($PA \leq 42.9\%$) will continue on clopidogrel. This value was determined as a significant cutoff for ischemic risk in prior studies. If the decision is made to proceed with percutaneous revascularization, patients assigned to remain on clopidogrel will receive 300mg clopidogrel loading dose in the cath lab, and then remain on 75mg po daily. Patients assigned to prasugrel will receive 60mg po loading dose, and then remain on 10mg po daily.

Telephone follow-up will be conducted after 6 months to assess for ischemic and bleeding events.

The enrollment and study process is depicted in a Fig 1.

We plan on enrolling 100 subjects, with 50 subjects randomized to each arm:

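### The stated power of 0.8 sets 20% against a 50% on-clopidogrel rate, but the randomised control arm is LTA-guided and also switches patients to prasugrel

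*Protocol*

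**What the plan says.** Section 5 (Statistical Considerations) starts from a 50% prevalence of MA ≥ 69 "in the general patient population with ACS on clopidogrel referred for cardiac catheterization according to previous studies". It continues: "It was assumed that switching to prasugrel would reduce the maximal clot strength in 60% of these patients with baseline MA ≥ 69", which brings the prevalence to 20%. The conclusion is: "Assuming a power of 0.8 and alpha 0.05 with a loss of 5% of follow-up, a sample size of 50 in each arm", 100 in total.

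Section 2.0 (Enrollment/Randomization) fixes the arms: "the patient will be randomized to either a TEG guided or LTA guided strategy", and "We plan on enrolling 100 subjects, with 50 subjects randomized to each arm". In the TEG-guided arm every patient with MA ≥ 69 goes to prasugrel. The LTA-guided arm has its own switching rule: "Patients in the LTA guided arm with high on treatment platelet reactivity to ADP" (PA > 42.9%) are assigned to prasugrel. For those not switched, "patients assigned to remain on clopidogrel will receive 300mg clopidogrel loading dose in the cath lab".

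The Introduction describes the comparator in the same way: "as a control group we will include a group of patients which will be assigned to prasugrel or clopidogrel therapy based on LTA measurements". The Specific Aims include comparing the two guided strategies. The primary endpoint is persistence of high clot strength on TEG 16-24 hours after the reload. The study purpose, at the end of the Introduction, treats the relation between high clot strength and LTA non-response as something the study will assess.

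**The concern.** The 20% is the expected result of the TEG-guided rule. The 50% is a prevalence before any study treatment, in patients on clopidogrel. It can stand for the LTA-guided arm at the endpoint only if almost no high-MA patient there exceeds the LTA cutoff and is switched, and almost none falls below 69 after the clopidogrel reload. The Protocol asserts neither. Its primary hypothesis, that high MA is partly a matter of inadequate P2Y12 inhibition, makes some overlap with LTA non-response plausible.

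A reader is likely to take 0.8 as the power of the randomised comparison. If the LTA-arm rate is well below 50%, a non-significant difference between strategies would look more informative than it is. The Protocol says its data may inform later trials of personalised therapy, and it supplies no figure from which to judge the loss.

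**Working it through.** **Inputs from the Protocol.** Section 5: 50% on clopidogrel; 60% response to switching; 20% afterwards; power 0.8; alpha 0.05; 5% loss; 50 per arm. Sidedness is not stated, so two-sided is assumed. Evaluable per arm: 50 × 0.95 = 47.5, taken as 47.

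**1. Where the 20% comes from.** 0.50 × (1 − 0.60) = 0.20. This requires every MA ≥ 69 patient to switch, which is the TEG-arm rule.

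**2. Reproducing 50 per arm.** For two independent proportions,

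n = [1.960 × √(2 × 0.35 × 0.65) + 0.842 × √(0.5 × 0.5 + 0.2 × 0.8)]² / 0.30² = 38.5 per arm.

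With continuity correction, n = (38.5/4) × [1 + √(1 + 4/(38.5 × 0.30))]² = 44.9, so 45. Allowing for loss, 45/0.95 = 47.4, so 48, which is close to 50. The calculation is sound as an unpaired comparison of 50% with 20%.

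**3. Does a before/after test explain 50?** Suppose 30% of TEG-arm patients convert from high to low and none rise. An exact McNemar test then needs at least 6 converters for p ≤ 0.05. Its power is 0.807 with 25 patients and 0.998 with 47. A correctly paired calculation would not lead to 50 per arm.

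**4. Power by LTA-arm rate.** 47 v 47, TEG arm 20%, exact binomial enumeration with rejection at p ≤ 0.05. No model of overlap is needed.

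| LTA-arm rate | Pearson chi-square | Fisher exact |
|---|---|---|
| 50% | 0.877 | 0.830 |
| 47% | 0.808 | 0.747 |
| 45% | 0.751 | 0.680 |
| 40% | 0.573 | 0.488 |
| 35% | 0.373 | 0.294 |
| 30% | 0.199 | 0.142 |

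Power of 0.80 needs an LTA-arm rate of at least 46.7% (chi-square) or 48.8% (Fisher).

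**5. What could bring the rate below 50%.** This step is illustration only; h and r are assumptions, not Protocol figures. Let h be the share of MA ≥ 69 patients who are also above the LTA cutoff. Let r be the share of high-MA patients left on clopidogrel who fall below 69. Apply the Protocol's 60% response to those switched, and let no MA < 69 patient rise:

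LTA-arm rate = 0.5 × [0.4h + (1 − h)(1 − r)].

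| h | r | LTA-arm rate | Chi-square / Fisher |
|---|---|---|---|
| 0 | 0 | 50% | 0.88 / 0.83 |
| 0.1 | 0 | 47% | 0.81 / 0.75 |
| 0.3 | 0 | 41% | 0.61 / 0.53 |
| 0.5 | 0 | 35% | 0.37 / 0.29 |
| 0.1 | 0.1 | 42.5% | 0.67 / 0.59 |
| 0.3 | 0.1 | 37.5% | 0.47 / 0.39 |

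If instead every LTA-high patient responded (r = 0), the rate at h = 0.3 would be 0.5 × 0.7 = 35%, with power 0.37 / 0.29.

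**6. Analysis limited to baseline MA ≥ 69.** About 0.5 × 47 = 23.5, taken as 24 per arm. The TEG-arm rate is 40%; the LTA-arm rate is 0.4h + (1 − h)(1 − r).

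| h | r | LTA-arm rate | Chi-square / Fisher |
|---|---|---|---|
| 0.3 | 0 | 82% | 0.88 / 0.81 |
| 0.5 | 0 | 70% | 0.59 / 0.47 |
| 0.3 | 0.1 | 75% | 0.73 / 0.62 |

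**The case against.** Section 5 never says that 50% is the LTA-arm rate or that 0.8 is the power of TEG versus LTA. The primary hypothesis is about switching drug and does not mention LTA, and the endpoint is worded by drug rather than by strategy. An unpaired formula applied to on-clopidogrel versus after-switching would give the same sample size, so reproducing 50 identifies the formula and not the groups. On that reading the fault is an unnamed contrast rather than a wrong comparator. This stands in part: the two-arm reading is an inference. It is nevertheless the natural one, because the size is given for each arm, patients are randomised 50 to each, and the aims name the comparison. On the other reading, the randomised comparison has no stated power at all.

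The overlap values come from outside the document. The Introduction also says that insufficient P2Y12 inhibition may only partly explain the risk from high clot strength, which is some ground for incomplete overlap. That is fair. Step 5 shows sensitivity and is not an estimate of the trial's actual power. Step 4 does not depend on it.

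Persistence can be read as applying only to patients high at baseline, and there 0.8 survives a moderate overlap, as at h = 0.3 with r = 0. That also stands, but section 5's 50% and 20% are whole-arm prevalences, and the subset too falls below 0.8 at h = 0.5, or at h = 0.3 with r = 0.1.

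The unseen analysis plan does not answer the point: the justification is given in the Protocol, and one of its inputs does not match the control arm described there.

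**Conclusion.** The concern holds. The sample size arithmetic is correct, but the 50% comparator is not a justified endpoint rate for either randomised arm, and no rate for the LTA-guided arm is given. As the power of TEG versus LTA, 0.8 is right only if that arm's rate is within a few points of 50%; at 40% the chi-square power is 0.57 and at 35% it is 0.37. These figures rest on 47 evaluable per arm, a two-sided test, a whole-arm analysis and the Protocol's own 20% in the TEG arm. How far the true LTA-arm rate lies below 50%, if at all, cannot be determined from the document.

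**What to change.** In section 5:

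1. Name the contrast to which the power applies. If 50% versus 20% was meant as before versus after switching, say so and give the between-arm power separately.
2. Replace the 50% comparator with the expected LTA-arm rate, under an explicit assumption about the overlap of MA ≥ 69 with PA > 42.9%. Because the study itself is to assess that relation, label the figure as an assumption.
3. Replace the unqualified 0.8 with the power of 50 per arm over a range of that rate. Suggested text: *With 47 evaluable patients per arm and 20% high clot strength in the TEG-guided arm, chi-square power (two-sided alpha 0.05) is 0.88, 0.75, 0.57 and 0.37 if the rate in the LTA-guided arm is 50%, 45%, 40% and 35%.*

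The cost is a rewording of section 5 and a less favourable stated power. Sample size, treatment rules and endpoint are unchanged. The change discloses the uncertainty; it does not restore power.
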